This interface will include data on both ICS and SABA inhaler use. The interface will also have flags to notify the office of under or overuse of inhalers, with a protocol in place to reach out to patients. We will also be assessing the factors associated with the feasibility and sustainability of the Remote Health Management Platform by the healthcare team. This will be done by weekly contact with the healthcare team, rapid cycle improvement of the web portal, and written assessments. Follow-up assessments through interview will be conducted at the end of the trial with health providers.

[figure not shown]

Figure 1. Study Arms

Participant Sites

The participant sites will be pediatric clinics in the Chicagoland Area. Each site in this proposed study has a strong history of research collaborations with [name], which includes the ability to recruit and retain patients in research studies.

We will be recruiting from at least four of the following sites:

- Children’s Healthcare Associates
- Chicago Family Asthma and Allergy
- Clark/Deming Resident Clinic (Lurie Children’s)
- Pulmonary Clinic (Lurie Children’s)
- Lurie Children’s Uptown Clinic

Study Design and Procedures

1. **Design:** We will conduct a randomized controlled trial comparing asthma inhaler use and asthma-related outcomes between children who either receive the Remote Health Management Platform (intervention) or Standardized Education (control) for asthma management. We will use a prospective cohort design to determine the effect of the intervention on the aforementioned outcomes.

We will enroll patients from Chicago pediatric clinics, as well as inpatient units at Lurie Children’s Hospital. At enrollment, we will randomize children to either the Remote Health Management Platform (intervention) group or the Standardized Education group (control).

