The Remote Health Management team (Propeller Health) utilizes telehealth concepts, including an FDA-approved sensor, mobile apps, predictive analytics, and feedback to help patients and providers better manage asthma.^{11,12} The sensor monitors the use of inhaled medications (ICS and SABA), capturing the date, time, and number of uses. The sensor transmits this information via Bluetooth to a paired smartphone or hub. The location of the event is also securely uploaded to the cloud if the sensor is connected to the Smartphone at the time the sensor is used. Data can be uploaded to the caregiver's smartphone and to the patient's web portal, which their healthcare team will have access to help overall management.¹³

The sensors will be distributed to participants by the study team. We will aim for participants to engage with the study team before going to the clinic or hospital so the device is ready to use at the time of their appointment. This will require the participants to call the research team and the consent being described over the phone to the participants. At their appointment and when the device is given, the participants will sign the consent.

6. Randomization

After recruitment, participants will be stratified by age, sex, and insurance status. They will then be randomly assigned to one of the two study arms.

After recruitment, participants will be stratified by age (4-7 vs 8-17), sex (M vs F), and insurance type (private vs. public), resulting a total of eight strata (stratum1: 4-7, M, Private, stratum2: 4-7, M, Public, stratum3: 4-7, F, Private, etc.). Since this is not a double-blind study and no centralized randomization system will be implemented, one randomization schedule will be generated for each site. Each randomization schedule will contain all eight strata. To ensure balanced treatment allocations within each stratum, 20 randomization blocks will be generated within each stratum. Each block has a block size of 4 with a random permutation of treatments A and B (eg, block 1=AABB, block2=ABBA, etc). Each site's randomization schedule will begin with a distinct randomization sequence number which is different from the subject ID number. For example, site 1's randomization schedule will begin with randomization sequence number 100001, site 2's randomization schedule will begin with randomization sequence number 2000001, etc.

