- b. Health providers will be interviewed about their experience using the web portal (Study Aim 3), using the data generated by the sensors, and managing pediatric asthma patients and their interaction with parents
- e. Health providers will be informed that the in-person, or telephone, interview will be audio-recorded. In-person interviews will be conducted at their clinic location in a private office.
- f. Interviews will last approximately 60 minutes and conducted by research staff.

Study Extension

Data analysis will begin 12 months after a participant is enrolled (beginning January 2018.). During the analysis period, we will also determine the feasibility of implementing the intervention more broadly throughout the healthcare system.

Study Subjects:

Eligible participants will be children 4-17 years old with moderate or severe persistent asthma, as diagnosed by their pediatrician, who are primarily seen for their asthma care at one of the participating clinical sites, and who have parents/caregivers willing to participate in this study. Participants will also be required to have received oral corticosteroids in the past year.

Study Enrollment:

Recruitment will occur by a research assistant at all sites. Scheduling of recruitment and participant screening will require the healthcare team to identify potential participants and then the RA either calling or mailing an informational pamphlet to the parents prior to their next appointment. Participants may also be recruited in the clinic by the RA, but will require the RA to follow-up with them via the telephone to properly install and utilize the Remote Health Management Platform. Participants may also be recruited through Lurie Children's Hospital Inpatient service after an asthma exacerbation. Only children who receive their primary care from one of the 5 study clinics will be permitted to be in the study. A member of the research team will work with hospitalists to recruit these individuals.

For the post-trial semi-structured interviews, only those participants who had previously responded that they were interested in further contact by the research team will be recruited. Study staff will contact potential participants for interviews by telephone and only schedule a time if participants remain interested after the interview study has been explained to them.

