# **Statistical Analysis:**

### Demographic and baseline characteristics:

Demographic and baseline characteristics including gender, age, race, ethnicity, and co-morbidities will be summarized for each treatment group and overall. The demographic and baseline characteristics summary will be based on all randomized subjects.

Baseline values for efficacy parameters (ACT, quality of life score, PAMSE) will also be presented for each treatment group and overall based on all randomized subjects.

For continuous variables, non-missing will be used to calculate the mean, median, SD, IQR, minimum and maximum by treatment group and overall. For categorical variables, the count and percentages of each possible value will be tabulated by treatment group and overall.

All comparisons of baseline characteristics between treatment groups will be adjusted for potential household clustering using robust standard errors. For continuous variables, comparability of treatment groups will be assessed using general linear models. For discrete variables, comparability will be assessed using the Cochran-Mantel-Haenszel general association test. P-values will be displayed as descriptive statistics of comparability in order to identify potential baseline imbalances with an alpha level of 0.05.

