# AIM 1. Determine factors influencing clinical and psychosocial outcomes.

Clinical and psychological outcomes of interest include the 12-month rate of asthma-related oral corticosteroid use, ED visits, and hospitalizations, as well as change in mean ACT scores (range of 0 to 27) from baseline to end line (12 months). Psychological outcomes of interest include quality of life score (range of 1 to 7), parental self-efficacy score, and the number of school days missed due to asthma. Potential predictors of outcomes include age (4 to 7 years vs. 8 to 17 years), gender (M vs. F), race/ethnicity (non-Hispanic white, non-Hispanic Black, Hispanic, vs. others), insurance status (private/public), and co-morbidities.

Each count variable (asthma-related oral corticosteroid use, ED visits, and hospitalizations) will be analyzed by mixed negative binomial regression analysis adjusting for treatment, all potential predictors, and including maximal random effect structures (i.e., slope and intercept as allowed by the model) of family and clinic. VIFs (variance inflation factors) will be computed for each predictor. Highly correlated predictors (i.e. predictors that can be well-explained by other predictors) will be dropped from the model to avoid multicollinearity issues. Model fit criteria, parameter estimates, and precision of parameter estimates will all be evaluated to select the most parsimonious model.

For each continuous primary outcome variable (i.e., ACT score), change-from-baseline score at each visit will be analyzed using mixed linear regression models, adjusting for treatment, time point, baseline score, all potential predictors, and including random effects (i.e., both slope and intercept) of family and clinic. A treatment by time interaction will be included to evaluate whether the effect of the treatment on the primary outcome varies by time point. VIFs will be investigated for each predictor, and those with high VIFs (VIF>=10) will be dropped from the model to avoid multicollinearity issues. An unstructured covariance (UN) matrix will be assumed. Model fit criteria, parameter estimates, and precision of parameter estimates will also be used to select the most parsimonious model. Model diagnostics will be performed to check model assumptions. All analyses will be performed using statistical analytic software Stata Version 15.1.

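### The ACT primary model puts random intercepts and slopes on 4 to 5 clinics and on families without naming the slope variable or the unstructured matrix, and leaves simplification to the data; fixed site effects would be simpler

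*SAP*

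**What the plan says.** The SAP, AIM 1 (repeated in the protocol's Statistical Analysis section), models change in ACT from baseline at each visit. The model has treatment, time point, their interaction, the baseline score and the predictors, "including random effects (i.e., both slope and intercept) of family and clinic". It adds: "An unstructured covariance (UN) matrix will be assumed". It then says: "Model fit criteria, parameter estimates, and precision of parameter estimates will also be used to select the most parsimonious model".

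The count outcomes get a softer version: "maximal random effect structures (i.e., slope and intercept as allowed by the model) of family and clinic". The feasibility qualifier in that phrase is absent from the ACT sentence.

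On the number of clinics, the protocol (Participant Sites) says "We will be recruiting from at least four of the following sites" and lists five. Its Study Enrollment section says "Only children who receive their primary care from one of the 5 study clinics will be permitted to be in the study". Under 6. Randomization, "one randomization schedule will be generated for each site", so treatment is allocated within site. For baseline comparisons the SAP already has a way of dealing with siblings: they are "adjusted for potential household clustering using robust standard errors".

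Neither document names the slope variable, the matrix that is unstructured, a degrees-of-freedom method, or an order in which terms would be removed if the model does not fit.

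**The concern.** A random intercept and slope for clinic ask the data for two variances and a covariance from 4 or 5 units. A family intercept and slope ask for three more parameters. If most families contribute one child, the data may hold no separate information on those three once the visit covariance is unstructured. Boundary estimates and convergence failures are then likely, and the analyst must simplify a primary model after seeing results. If the clinic slope is on treatment, the standard error of the treatment effect also depends on a variance estimated from 4 or 5 clinic differences.

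**Working it through.** **Inputs.** From the protocol: 4 to 5 clinics; 250 children randomised 1:1; 20% dropout; two-sided alpha 0.05; 85% power (Sample Size Determination). Follow-up surveys are at 1, 3, 6, 9 and 12 months in the SAP (five visits), while the protocol's outcome table omits month 1 (four visits). Assumed: equal clinic sizes, balanced arms within clinic, residual SD of 1, and the ICCs and heterogeneity shown below.

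**1. The plan's own sample size.** It rests on a binary exacerbation rate, 0.545 against 0.75, not on ACT. With a Wald test on the log odds ratio:

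n per arm = (1.960 + 1.036)² × [1/(0.545 × 0.455) + 1/(0.75 × 0.25)] / 0.9181² = 8.978 × (4.033 + 5.333) / 0.8430 = 99.8.

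The total is 199.5, and 199.5/0.80 = 249.4, so 250. The figure reproduces. It contains no ACT difference, no ACT SD and no allowance for clustering. The ACT figures below therefore use a generic effect with noncentrality 1.960 + 1.036 = 2.996 (85% by z) and 250 × 0.80 = 200 evaluable children.

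**2. Family terms, if the unstructured matrix is the visit-level residual and the slope is on linear time.**

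| Post-baseline visits | Residual matrix | Family | Clinic | Total | Rank, one child per family | Rank with a sibling pair |
|---|---|---|---|---|---|---|
| 5 | 15 | 3 | 3 | 21 | 18 | 21 |
| 4 | 10 | 3 | 3 | 16 | 13 | 16 |

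With one child per family, all three family parameters are absorbed by the residual matrix. Only siblings separate them.

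**3. Precision of a clinic variance.** Taking clinic effects as if observed without error, the 95% interval is the estimate times (K − 1)/χ², using the 97.5% and 2.5% points of χ² on K − 1 df:

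- K = 4: 3/9.348 = 0.32 to 3/0.2158 = 13.9.
- K = 5: 4/11.143 = 0.36 to 4/0.4844 = 8.3.

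The probability that the clinic intercept variance is estimated as zero is 42-43% at an assumed ICC of 0.01 and 14-16% at 0.05.

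**4. Power if the clinic slope is on treatment, with no true heterogeneity.** The variance of one clinic's treatment difference is v = 2/n, with n children per clinic-arm: 2/25 = 0.08 (K = 4) or 2/20 = 0.10 (K = 5). In the balanced case, SE² = max(s², v)/K, where s² is the observed variance of the K differences. Results from 400,000 simulated trials and from the noncentral t:

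| Analysis | 4 clinics | 5 clinics |
|---|---|---|
| Fixed site, z | 85% | 85% |
| Random clinic slope, z | 77% | 78% |
| Clinic differences, t on K − 1 df (correctly sized) | 53% | 62% |
| Slope variance estimated as zero | 61% | 59% |

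A smaller simulation with fitted mixed models (150 runs per setting, some with heterogeneity) gave average power of about 71% for the clinic slope by z, and about 83% each for fixed site and for a clinic random intercept alone. Between 74% and 87% of slope fits were singular or did not converge, a rate that depends on the optimiser.

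**5. Power if the clinic slope is on linear time.** With arms balanced within clinic, a clinic intercept and time slope largely cancel from the treatment contrast. The cost is close to nil.

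**6. Cost of fixed site effects.** At noncentrality 2.996 with 190 to 196 residual df, power is 84.6% to 84.7%, a loss of 0.3 to 0.4 points from 85%.

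**7. Fixed site under true heterogeneity.** Suppose the treatment effect varies between clinics with SD 0.3 residual SD around a mean of zero. Judged against a wider population of clinics, the fixed-site test has type I error 2 × [1 − Φ(1.960 × √(v/(v + 0.09)))]: 17.9% for K = 4 and 15.5% for K = 5.

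**The case against.** The strongest reply is that the harm depends on readings the SAP does not fix. The model is longitudinal, so a slope on time is at least as natural as one on treatment, and then little power is lost. A reader might infer that the model as written costs power outright; the documents do not support that. Nor can any loss be stated in ACT units.

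The unstructured matrix may be that of the random effects. The family argument then weakens, but the problem of few clinics stays.

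The parsimony clause, read generously, lets the analyst drop an unsupported slope, so the full structure is not strictly mandatory. That stands, but the clause chooses on estimates and precision and sets no order. It therefore concedes that the primary model will be picked from the data.

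Two stronger readings should be resisted. A reader might attach K − 1 degrees of freedom to the standard error floored at v and obtain much lower power than in the table. That test has a true type I error of only 0.1% to 0.4%, and nothing in the documents prescribes it. A reader might also charge the random-slope z-test with inflated type I error under heterogeneity. By the same yardstick the fixed-site test is worse (15-18%), so this is no argument for the change.

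Finally, a clinic random intercept alone performs about as well as fixed site. The choice between those two is a preference.

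**Conclusion.** The point holds as a defect of specification in a primary analysis. The clinic variances cannot be estimated usefully from 4 or 5 clinics on any reading. The family terms are not identifiable without siblings if the unstructured matrix is the residual one. What replaces the stated model is left to the data.

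The power loss is conditional: about 7 to 8 points by z-test (85% to 77-78%), or 23 to 32 points with the correctly sized small-sample test (85% to 62% or 53%), if the slope is on treatment and effects are homogeneous; near nil if it is on time. This assumes equal clinics, 200 evaluable children and a generic 85%-power effect.

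The count models are less exposed, because their wording already yields to what the model allows. The change is worth making because it is cheap and suits randomisation by site, not because the present model is shown to be invalid.

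**What to change.** In the SAP's ACT model:

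- fit clinic as a fixed effect, with no clinic slopes;
- state that the unstructured matrix is the visit-by-visit covariance within child;
- handle siblings by family-clustered robust standard errors, as the SAP already does at baseline, or by a family intercept only;
- remove fit-based selection of the primary model, and name the degrees-of-freedom method;
- show treatment effects by clinic descriptively.

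Use fixed site effects and family-clustered robust standard errors in the negative binomial models too.

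If the sponsor prefers random effects, the SAP should name the slope variable, the matrix, the degrees-of-freedom method and an ordered fallback.

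The cost is SAP wording, 3-4 extra parameters and 0.3 to 0.4 points of power. Inference then applies to the participating clinics only. The 15-18% error rate shows why it should not be presented as holding for clinics in general.

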# Missing data and sensitivity analyses:

Missing data will be handled using Multiple Imputations. Sensitivity analyses will be conducted using SAS procedures PROC MI and PROC MIANALYZE. Other sensitivity analyses may be performed if appropriate.

AIM 2. Enhance parental management through improved inhaler use.

After the patient's enrollment visit, parents will be contacted via email or phone at 1, 3, 6, 9, and 12 months to complete a REDCap survey. Descriptive statistics (frequencies and percentages) of each quantitative question will be summarized at each time point and associations between outcomes and demographic predictors will be analyzed by Chi-squared test. Qualitative data will be coded and analyzed by theme analysis.

AIM 3. Improve management by physician and clinical team.

On a biweekly basis, we will collect quantitative data from clinics on the number of time physicians' follow-up with patients and the follow-up outcome. The research team will know exactly how many alerts physicians are receiving, and how physicians are following-up with patients from the Propeller dashboard. The data from the Propeller dashboard will be summarized and associations between outcomes and clinic predictors will be analyzed by Chi-squared test. Clinicians will also be contacted at 1, 3, 6, 9, and 12 months through REDCap surveys to determine if the data is helping them with management and aspects of the platform they like and dislike. Descriptive statistics (frequencies and percentages) from surveys will be summarized at each time point and associations between outcomes and clinic predictors will be analyzed by Chi-squared test.

Qualitative data will be coded and analyzed by theme analysis.

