After the patient's enrollment visit, parents will be contacted via email or phone at 1, 3, 6, 9, and 12 months to complete a REDCap survey. Each quantitative survey item will be summarized using descriptive statistics such as frequencies and percentages along with any corresponding measures of spread. Qualitative data will be coded and analyzed by theme analysis.

The following questions will be asked:

Quantitative Questions:

1. How often do you check the sensor system?
 - More than once a daily
 - Daily
 - Once a week
 - More than once a week
 - Every other week
 - I don't check the Propeller Sensor (*If selected, participants will only answer question 1 and 5*)
2. How often in the past week did you receive useful asthma information through the sensor system?

- Once
 - Twice
 - Three or more times
 - I did not receive useful asthma information through the sensor system
3. How helpful is the sensor system in managing your child's asthma?
- Extremely helpful
 - Very helpful
 - Helpful
 - A little helpful
 - Not helpful
 - I have not checked the sensor system
4. What do you enjoy most about the sensor system?
- Easy to use
 - Ability to track inhaler use
 - Asthma Education cards
 - Other: *fill in the blank*
 - Nothing
5. Do you have any issues regarding the sensor system?
- *Comment Box*

AIM 3. Improve management by physician and clinical team.

On a biweekly basis, we will collect quantitative data from clinics on the number of time physicians' follow-up with patients and the follow-up outcome. The research team will know exactly how many alerts physicians are receiving, and how physicians are following-up with patients from the Propeller dashboard. The data from the Propeller dashboard will be summarized with descriptive statistics. Clinicians will also be contacted at 1, 3, 6, 9, and 12 months through REDCap surveys to determine if the data is helping them with management and aspects of the platform they like and dislike. Qualitative data will be coded and analyzed by theme analysis.

The following questions will be asked:

Quantitative Questions:

1. In the past week, how many times did you check the propeller dashboard?
 - Once time
 - Twice
 - 3 or more times
 - Zero
2. Are the Propeller Dashboard flags useful to you?
 - Yes
 - No
3. In the past week, how many times did you have to follow-up with patients due to alerts you received regarding the over use of Albuterol?
 - Once
 - Twice
 - 3 or more times
 - Zero

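### The SAP's chi-squared test of the caregiver survey ignores the order of items 1 to 3; an ordinal model that allows for repeated answers would be a cheap improvement to an exploratory analysis

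*SAP*

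**What the plan says.** SAP, AIM 2: "parents will be contacted via email or phone at 1, 3, 6, 9, and 12 months" to complete the survey. "Descriptive statistics (frequencies and percentages) of each quantitative question will be summarized at each time point", and in the same sentence "associations between outcomes and demographic predictors will be analyzed by Chi-squared test". The SAP does not name the type of chi-squared test, list the demographic predictors for this aim, or state an alpha or multiplicity rule for it. It gives no method for ordered answers, no fallback for sparse tables and no way of handling several answers from one caregiver.

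Protocol, Statistical Analysis, AIM 2, on the same survey: "Each quantitative survey item will be summarized using descriptive statistics such as frequencies and percentages along with any corresponding measures of spread". No test is mentioned.

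The protocol prints four closed items and a comment box:
- Item 1, "How often do you check the sensor system", has six options on a frequency scale. The last is not checking at all, and two options in the middle are printed out of order.
- Item 2, "How often in the past week did you receive useful asthma information through the sensor system", has four options, from none to three or more.
- Item 3 grades helpfulness in five steps, with a sixth option for people who have not looked at the system.
- Item 4 asks what is liked most; it has five options and no order.

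Caregivers who never check skip items 2 to 4. The sensor questions belong to the intervention-arm survey; the control arm has a different one (protocol, Timeline and Appendices).

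The nearest predictor list is in SAP, AIM 1: "Potential predictors of outcomes include age (4 to 7 years vs. 8 to 17 years), gender (M vs. F), race/ethnicity" (four groups), "insurance status (private/public), and co-morbidities".

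**The concern.** A Pearson test treats the options of a graded answer as interchangeable labels. It spreads its sensitivity over every possible pattern of difference, when the pattern of interest is a shift up or down the scale. Real differences in uptake by age, sex, insurance or race would therefore be harder to detect than they need be.

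Tests on several items, predictors and possibly months, with no error control and no exploratory label, can also turn up chance differences that are then read as predictors of feasibility. Utilization and feasibility are stated interests of Aim 2, and the protocol's Study Extension section uses the analysis period to judge wider implementation.

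Finally, the protocol and SAP disagree on whether these items are tested at all.

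**Working it through.** **Responders.** The documents give no figure for the Aim 2 tests, so the number of responders comes from the sample size section of the protocol, which reproduces.
- Odds ratio = (0.545/0.455)/(0.75/0.25) = 0.3993; log = -0.9181.
- n per arm = (1.960 + 1.036)² × [1/(0.545 × 0.455) + 1/(0.75 × 0.25)] / 0.9181² = 99.8, so 100.
- 100/0.8 = 125 per arm, 250 in total.

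After the planned 20% drop-out the intervention arm has about 125 × 0.8 = 100 caregivers. Items 2 to 4 will have fewer because of the skip rule.

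**Power.** The documents give no answer distributions or predictor splits, so these are assumptions: 50 against 50 responders, a common odds ratio of 2 across the cut-points, two-sided 0.05. Simulated power:

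| Assumed answers | Pearson | Rank test | Loss (points) |
|---|---|---|---|
| 6 options, even | 29% | 51% | 23 |
| 6 options, skewed | 23% | 47% | 24 |
| 5 levels, 0.25/0.25/0.25/0.15/0.10 | 28% | 48% | 20 |
| 4 options, even | 34% | 49% | 15 |
| 4 options, skewed | 28% | 43% | 14 |

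Losses are taken before rounding. The five-level row corresponds to item 3 with its non-use option left out. For that row at an odds ratio of 2.5 the figures are 47% and 71%.

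**Sparsity.** Item 1 by race has 6 × 4 = 24 cells, so the mean expected count is 100/24 = 4.2. With assumed margins of 0.10/0.30/0.20/0.20/0.10/0.10 (answers) and 0.30/0.35/0.25/0.10 (race), 15 of 24 cells (62.5%) have an expected count below 5, and the smallest is 100 × 0.10 × 0.10 = 1.0. The simulated type I error of Pearson's test in that table is nevertheless about 4.6 to 4.9%. Over all 20 item-by-predictor tables, the average is 4.9% with even answers and 4.5% with skewed answers. With the same item 1 margins and a 50:50 binary predictor, the smallest expected count is 50 × 0.10 = 5.0 and no cell falls below 5.

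**Number of tests.** Tests = items × predictors × months; expected chance findings = 0.05 × tests if every null hypothesis is true.

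| Reading | Tests | Expected chance findings |
|---|---|---|
| 4 items, 5 predictors, 5 months | 100 | 5.0 |
| 4 items, 4 predictors, 5 months | 80 | 4.0 |
| Items 1 to 3, 5 predictors, 5 months | 75 | 3.75 |
| Items 1 to 3, 4 predictors, 5 months | 60 | 3.0 |
| Items 1 to 3, 3 predictors, 5 months | 45 | 2.25 |
| Not repeated by month | 9 to 20 | 0.45 to 1.0 |

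**Pooling the months.** If the tests are not repeated because the five months are put in one table, each caregiver contributes up to five answers that share one value of the predictor. In a simulation with 100 caregivers, five months and an assumed latent within-caregiver correlation of 0.3, 0.5 or 0.7, Pearson's false-positive rate was about 13%, 22% or 31%.

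**The case against.** A reader might infer that the sparse tables invalidate the test. The documents give no basis for that, and the check points the other way: in the worst table the error rate is close to 5%, and over all tables the test is on average nominal or mildly conservative. A low expected count is a reason to state an exact fallback if any chi-squared test is kept; it does not show excess false positives. Nor is sparsity general, since age, sex and insurance are binary.

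A reader might also infer about five chance findings. That is the top of the range. It needs the nominal item 4, the whole Aim 1 predictor list (including co-morbidities, which are not demographic), a test at every month, and an alpha of 0.05. The SAP ties the monthly timing to the descriptive summary, and monthly testing is only the natural reading of the rest of the sentence. An alpha of 0.05 is stated for the baseline comparisons and the sample size, not for this aim.

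Further points stand. The SAP does not say the test is the unordered one. Only items 1 to 3 are ordered, and item 3 has an option off the scale. The power figures depend on assumed distributions, and at an odds ratio of 2 even the rank test misses about half of real differences. They compare single-time tests, so the power of the longitudinal ordinal model itself has not been shown. The survey measures feasibility and acceptability, and no sample size rests on it.

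What the objection does not remove is that order is discarded in three of four items, that neither the monthly nor the pooled reading is handled, and that the protocol and SAP differ.

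**Conclusion.** The point holds as an improvement to an exploratory analysis. For items 1 to 3, replacing Pearson's test with an ordinal method recovers roughly 15 to 25 points of power, given about 100 responders, an evenly split binary predictor, proportional odds and an odds ratio of 2. The direction was the same for four, five and six options and for even and skewed answers.

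On multiplicity, the supportable statement is about 2 to 5 chance findings from 45 to 100 monthly tests at an assumed alpha of 0.05, and 1 or fewer if tests are not repeated by month. If the months are pooled without allowing for repeated answers, the independence assumption fails and the error rate rises; how far depends on the within-caregiver correlation, which the documents do not give.

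The documents do not support saying that the chi-squared approximation breaks down. No primary outcome, treatment comparison or sample size is affected, so the point is one to consider, not a condition of going ahead.

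**What to change.** In SAP, AIM 2:
- For items 1 to 3, replace the chi-squared tests with one proportional-odds model per item and predictor, fitted across all months with terms for month and the predictor. Allow for repeated answers by a caregiver random effect or by standard errors clustered on caregiver.
- List the demographic predictors. With three to five of them, 3 × 3 = 9 to 3 × 5 = 15 estimates replace up to 100 tests.
- Fix in advance the order of the item 1 options, and say whether the non-use answers (not checking, nothing useful received, system not looked at) are placed on the scale or excluded.
- Report odds ratios with confidence intervals, labelled exploratory. Describe item 4 only.
- Reconcile the protocol and SAP, so that both either include this exploratory analysis or confine themselves to description.

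The cost is wording: no new data and no design change. The downside is the proportional-odds assumption, which should be checked, and a judgement about the non-use answers. If a chi-squared test is kept anywhere, state an exact alternative for sparse tables.
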